3. INCLUSION CRITERIA

1. Male or female 40-70 years old diagnosed with clinically evident fine (mild) to moderate depth periorbital wrinkling
2. Willingness and ability to comply with all required study activities and protocol requirements.
3. The subject is able to provide written informed consent and perform the study's activities according to HIPAA guidelines and/or Israeli law, depending on each specific study site.

4. EXCLUSION CRITERIA

1. The subject may not undergo treatment by the Tixel or comparator device according to the device's contra-indications for use, as defined in the User Manual and in the Instructions for Use and by any other labeling of the device.
2. Female subjects who are pregnant, or planning to become pregnant, or have given birth less than 3 months ago or are lactating.
3. Subjects with significant exposure to critical amounts of ultraviolet light (Sun tan).
4. Subjects who have had the following treatments:
 - a. a prior cosmetic procedure to improve facial rhytides (i.e., rhytidectomy, periorbital or eyelid/eyebrow surgery, brow lift, CO2/Erbium/similar laser/fractional resurfacing, radiofrequency treatment) within 12 months
 - b. prior facial treatments with laser, surgical, chemical or light based facial treatments within the previous 6 months, such as for botulinum toxin injections, retinoid, microdermabrasion or prescription level glycolic acid treatments
 - c. Injectable filler in area to be treated within 9 months of investigation.
 - d. permanent facial implant
5. Any subject who have visible scars that may affect evaluation of response and/or quality of photography.

6. Subjects with any type of active cut, wound, inflammation, lesion (benign, premalignant or malignant) or active bacterial, viral, fungal, or herpetic infection on the skin on the designated treatment sites or in close proximity to it.
7. Existing or history of the following (when discussing skin conditions, refers only to the periorbital sites):
 - a. skin malignancy, or any diagnosis of suspected malignancy
 - b. Collagen or vascular or bleeding disease
 - c. Immunosuppression or autoimmune disease
 - d. Erythema with or without blistering
 - e. History of post inflammatory hyperpigmentation.
 - f. Active Acne Vulgaris, HSV-1, or any existing skin condition/disease that in the investigator's opinion would interfere with the evaluation of the safety of the study treatment.
 - g. Any skin pathology which can induce bullous lesions, urticaria, or demonstrate a Koebner phenomenon (psoriasis, lichen planus, etc.).
 - h. Any disease that inhibits pain sensation
 - i. History of keloid formation, or hypertrophic scarring
 - j. Conditions affecting healing rate (i.e. diabetes mellitus I or II, vascular condition, etc.)
 - k. neuromuscular disorders
8. Subjects who have used, within 30 days, any medication that can cause dermal hypersensitivity or affect skin characteristics (i.e. topically applied Retinoids, Hydroquinone, Chemical peel of any strength: glycolic acid, lactic acid, salicylic acid)
9. Subjects who have used, systemic treatment which may induce dyspigmentation, such as amiodarone, clofazimine, minocycline or chloroquine.
10. Subjects currently taking or have taken an oral retinoid in the past six months (risk of scarring with therapy); Subjects currently taking long-term oral steroid treatment (causing fragility of the skin, risk of hematoma and bullae formation); Subjects taking Isotretinoin (Accutane or Roaccutane) within past 12 months.
11. Concurrent therapy that, in the principal investigator's opinion, would interfere with the evaluation of the safety or efficacy of the study treatment.
12. Subjects who anticipate the need for surgery or overnight hospitalization during the study.

13. Enrollment in any active study involving the use of investigational devices or drugs.
14. Any other cause per the principal investigator's discretion.

5. SUBJECT SELECTION: NUMBER OF SITES/INVESTIGATORS

There will be two investigational sites participating in this study, including one site in the U.S. and one in Israel.

5.1. Number of Subjects

A total of 82 subjects will be recruited to the study. They will be randomly split to two separate arms (41/arm) in each site, and undergo periorbital fractional treatments.

5.2. Study Arms

Subjects will be randomly assigned to one of the following groups:

- **Group I:** Tixel
- **Group II:** The ResurFX Non-Ablative Laser with the M22 device by Lumenis (1565 nm)

5.3. Intended Population

Male or female 40-70-year-old diagnosed with clinically evident periorbital wrinkling.

At least one of each Fitzpatrick skin type I to IV must be included in the study. In addition to this definition, all Fitzpatrick skin types (I-VI) may participate in the study. For clarity's sake, it is emphasized that not every site must have all skin types I-IV, but the entirety of the study's population.

6. STUDY DESIGN

The study is designed to explore the safety and effectiveness of the Tixel, a novel fractional device, in treatment of periorbital wrinkles in comparison to a currently market-available product, which applies fractional treatment. The study is designated to compare between the effect of a currently available fractional pulsed laser modality (the "comparator"), market-cleared in the US for the said purpose, and the Tixel.

This is an interventional, double-arm, controlled, randomized, prospective, multi-center (US, Israel), clinical study with single-blinded evaluation. The Tixel treatment results will be compared to a laser modality indicated for the same purpose.

7. PROCEDURE

Prior to beginning treatment, the subject will be given post-care instructions regarding skin care after treatment. Once the post-care instructions are reviewed with the subject, treatment may commence.

The subject's face should be gently cleansed with water and soap (hypoallergenic allowed) or any other cleansing materials customary for use prior to fractional treatment sessions, in order to remove any excess material from the skin such as natural oil, mascara clumps, etc. No materials with active ingredients shall be used in order to avoid interference with the study's objectives. All materials applied shall be documented in the CRF including method of application.

The study team member performing the cleansing shall be responsible for closely examining the subject's facial skin to ensure it is clean and dry. In case other cleaning procedures are customary in the study sites, they are acceptable as long as supervised and approved by one of the study's investigators, and as long as they are performed uniformly on the entire periorbital site and its immediate peripherals.

8. STUDY BLINDING

This study is single blinded with limited access to the randomization code. Every effort will be made to retain the integrity of the blinding. Subjects will be randomized post-screening.

The treatment each subject shall receive will not be disclosed to any of the investigators until subject screening and enrollment is complete. The same shall apply regarding study site personnel, subjects, monitors, or the Sponsor staff except as required for the purposes of conducting this study.

The blinded evaluators shall not be exposed to the information, as well, in order to keep their assessment objective.

9. STUDY FLOWCHART AND FOLLOW-UP ASSESSMENTS

Procedure	Visit 1	Visit 2	Visit 3	Visit 4	Visit 5	Visit 6	Visit 7	Visit 8
	Treatment 1 ^c	Treatment 2	Treatment 3	Treatment 4 Optional	Treatment 5 Optional	1 month Follow-up 1	3 months Follow-up 2	6 months Follow-up 3
	T ₀ ^f (± 5d) ± Δ ^{ef}	T ₀ + 4w (± 5d) ± Δ	T ₀ + 8w (± 5d) ± Δ	T ₀ + 12w (± 5d) ± Δ ^e	T ₀ + 16w (± 5d) ± Δ ^e	T ₀ + 20w (± 8d) ± Δ ^e	T ₀ + 28w (± 8d) ± Δ ^e	T ₀ + 42w (± 8d) ± Δ ^e
Max duration	-	4w+5d	8w+10d	12w+15d	16w+20d	20w+25d	28w+33d	40w+41d ~ 47w
Min duration	-	4w-5d	8w-10d	-	-	12w-15d	20w-23d	32w-29d ~28w
Subject Screening, Enrolment Procedure & Informed Consent ^g , Post treatment care instructions	X							
Facial dermatological skin examination	X	X	X	X	X	X	X	X
Inclusion/ Exclusion criteria	X							
Medical/Surgical history	X							
Demographics	X							
Limited Physical examination ^a	X							
Concomitant Therapy/Medication	X _b	X	X	X	X	X	X	X
Verbal Inquiry regarding pregnancy	X	X	X	X	X	X	X	X
Photography of Treatment Area(s) – prior to treatment	X (baseline)	X	X	X	X	X	X	X
Photography of Treatment Area(s) – After treatment			X					
Investigational/Comparator Device Treatment	X	X	X	X	X			
Subject experience and satisfaction questionnaire	X		X*	X*	X*	X*		X

Procedure	Visit 1	Visit 2	Visit 3	Visit 4	Visit 5	Visit 6	Visit 7	Visit 8
	Treatment 1 ^c	Treatment 2	Treatment 3	Treatment 4 Optional	Treatment 5 Optional	1 month Follow-up 1	3 months Follow-up 2	6 months Follow-up 3
GAIS Assessment		X	X	X	X	X	X	X
FWCS Assessment	X _f	X	X	X	X	X	X	X _f
WAS Assessment	X _f	X	X	X	X	X	X	X _f
Subject VAS Pain assessment	X	X	X	X	X			
Subject Assessment Questionnaire (regarding downtime, skin erythema, redness and scabs)		X	X	X	X	X		
Adverse Events	X	X	X	X	X	X	X	X
Subject Compliance	X	X	X	X	X	X	X	X
Post Treatment Care Instructions	X	X	X	X	X			

- A limited physical examination will be performed at Screening to support the eligibility determination. System review will include general appearance, and a routine physical examination, according to the standard of care and as customary for fractional treatments.
- At Screening, the review of concomitant medications should include those taken within the past year.
- All assessments on treatment days are to be performed prior to treatment; the assessments performed prior to Treatment 1 will be designated as Baseline.
- Treatment sessions 4 & 5 are optional for both treatment options, based on the investigator's assessment of the subject's response.
- The sign Δ signifies the possibility of the change of the study's duration. Any delay of this sort will be documented and explained in writing.
- Blinded assessment performed in addition to physician assessment. Shall be performed at the end of the subject's activities.
- First visit may be split into two separate visits: part I: screening, enrollment and informed consent, and part II: rest of visit content (see in **שוויה! מקור ההפניה לא נמיצה.**)

* The * symbol is designated to show that filling out the Subject experience and satisfaction questionnaire is optional and should only be performed in one of the visits marked by the symbol. This is because it may be determined in a specific treatment visit (no. 4 or no. 5) that no more treatments are required. Therefore, the questionnaire

should be filled out in the last treatment visit or in a following visit. For convenience purposes, it is also allowed to have the questionnaire filled out by the subject in the first follow-up visit.

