technology that has been designed to provide a comparable clinical effect as a pulsed laser, which can be used as a treatment modality for a variety of applications, including fractional treatment of human skin. The Tixel technology is based on the supply of contact-transferred heat from a high temperature (385°- 400°C) metal element (called a “tip”) consisting of an array of miniature pyramids. The tip creates a thermal effect in the tissue (usually 200-300 microns deep) in the tissue within 5 – 16 milliseconds, thus mimicking the pulsed laser action. The tip thermally generates a matrix of coagulation sites (or “micropores”) on the skin. Dermal heating and coagulative effect that occur during the treatment session provide for dermal remodeling and collagen restructuring that promote wrinkle reduction and general wrinkle appearance improvement.

Protocol Number:

CLN 0460

Study Design:

Prospective, single-blinded, randomized, controlled study

Number of Study Sites:

2

Study Population:

Male and female subjects between 40-70 years of age (inclusive) diagnosed with clinically evident periorbital wrinkles

Study Treatment:

Subjects will be treated with the Tixel for periorbital wrinkles every 4-6 weeks for a series of 3 to 5 treatment sessions followed by 3 follow up sessions (see flowchart for full schedule details and options). The number of treatments may vary from subject to subject and shall be determined by the investigators' assessment of the subjects' improvement.

The minimal estimation for study duration per subject is 27 weeks, and the maximal estimation is 47 weeks (please see study flowchart for further details).

Comparator Treatment:

The ResurFX Non-Ablative Laser with the M22 device by Lumenis (1565 nm) for treatment of periorbital wrinkles

2. STUDY OBJECTIVES:

To demonstrate the safety and performance of the Tixel fractional system for treatment of periorbital wrinkles in comparison to the selected market-cleared comparator.

2.1.Primary Outcome Endpoints:

Each subject shall be assessed based on FWCS. Each subject shall contribute two separate data time points to the study.

2.2.Safety

Physical and dermatological examinations, erythema, and adverse events (such as PIH, burns, etc.) monitoring will be performed and assessed at every visit (including follow up visits).

2.3.Effectiveness/Performance

Effectiveness/Performance shall be assessed and quantified by 3 blinded assessors.

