The following assessment method will be applied by the blinded assessors (by images only):

- FWCS - Fitzpatrick Wrinkle Classification System

2.4.Secondary Outcome Endpoints

The following criteria will be assessed as secondary outcome endpoints:

- Secondary Effectiveness/Performance shall be assessed and quantified by a handling physician (one of the team's investigators of the study).

The following assessment methods will be applied (frontal clinical assessment or by images):

- FWCS - Fitzpatrick Wrinkle Classification System
- GAIS - Global Aesthetic Improvement Scale Assessment
- WAS - 5-point Wrinkle Assessment Scale
- Subject Experience
- Pain Level VAS Scale
- Subject Subjective Downtime Assessment

- Subject redness, edema and crust assessment (time for resolution)
- End-User Experience Assessment

Clinic Visits Baseline, 4wk, 8wk, (optional 12wk and 16wk), 20wk, 28wk, 42wk

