11.3 Secondary endpoints

All parameters below will be summarized at baseline condition and all post-baseline conditions. The change from baseline to the last follow-up will be analyzed using Wilcoxon paired test.

The following secondary endpoints will be summarized in appropriate tables by device and visit:

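### The flowchart footnote puts every treatment-day assessment before treatment, so VAS pain, scheduled only on treatment days, does not measure treatment pain as written

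*Combined protocol and SAP*

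**What the plan says.** The notes under the section 9 flowchart state: "All assessments on treatment days are to be performed prior to treatment; the assessments performed prior to Treatment 1 will be designated as Baseline". No exception is written.

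The flowchart row "Subject VAS Pain assessment" is marked at Visits 1 to 5, the three fixed and two optional treatment visits. It is blank at the follow-up visits, 6 to 8.

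Section 2.4 lists "Pain Level VAS Scale" among the secondary endpoints and section 11.3.1.5 repeats the name. Neither says when the score is taken or what period it covers. Section 7 (Procedure) describes preparation before treatment and does not mention pain.

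For the secondary endpoints, section 11.3 says: "All parameters below will be summarized at baseline condition and all post-baseline conditions". It then tests the change from baseline to the last follow-up with a paired Wilcoxon test. Section 11.3.1.9 compares changes within each device and between devices.

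**The concern.** Pain is one of the endpoints compared between the two devices, and the Investigational Product paragraph presents greater patient comfort as a design aim of the Tixel. The score is useful only if it refers to the pain of a session.

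A site that obeys the footnote asks about pain before the device is applied, about four weeks after the previous session. A site that asks afterwards, as common sense suggests, departs from the written rule and has no stated time to follow. With two sites in two countries, practice could differ. Mixing pre-session and post-session scores would dilute any difference between devices. The site adjustment in section 11.2 is written for the primary endpoint, not for the secondary comparisons. Session pain that is not recorded at the time cannot be recovered later.

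**Working it through.** The plan states no figure on this point, so there is none to reproduce. The check counts how many sessions each reading of the VAS row can score.

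**Inputs**
- Number of sessions k per subject: 3, 4 or 5 (Study Treatment paragraph; flowchart).
- VAS: one score at each treatment visit, so k scores, with none at Visits 6 to 8 (flowchart).
- Subject questionnaire on downtime and skin reactions: Visits 2 to 6 (flowchart).
- Timing rule: all treatment-day assessments come before treatment (flowchart footnote).

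**Sessions captured under the footnote**
- VAS as current pain: each score precedes that day's session, so 0 of k are captured.
- VAS as recall of the previous session (an assumption): the Visit 1 score has no earlier session, and each later score covers the session before it, so k − 1 of k are captured.
- Subject questionnaire, for comparison: one follows each session, at the next treatment visit or at Visit 6, so k of k are covered.

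| k | VAS, current pain | VAS, recall | Questionnaire |
|---|---|---|---|
| 3 | 0 of 3 | 3 − 1 = 2 of 3 | 3 of 3 |
| 4 | 0 of 4 | 4 − 1 = 3 of 4 | 4 of 4 |
| 5 | 0 of 5 | 5 − 1 = 4 of 5 | 5 of 5 |

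The layout shows what was probably intended. The VAS row has the same marks as the device-treatment row (Visits 1 to 5), while the retrospective questionnaire is moved one visit later. If VAS were recall, it should have been moved too. Same-session pain is the likely intention, and the footnote rules it out.

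**The section 11.3 analysis applied to VAS**

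Change = (score at last follow-up) − (score at baseline).
- First term: no VAS is scheduled at Visits 6, 7 or 8, so it is missing for every subject.
- Second term: a score taken before Treatment 1 measures no treatment. A score taken after Treatment 1 is session-1 pain and is not Baseline under the footnote, which gives that name only to assessments made before Treatment 1.

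Reading last follow-up loosely as the last available VAS does not help. With post-session scores the change would be session k minus session 1, which shows whether pain rises or falls over the course. Two devices with steady but quite different pain would both show zero change. The between-device comparison in section 11.3.1.9 is also written in terms of changes, so it has the same defect.

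**The case against.** The strongest reply is that the footnote was never meant to govern pain. By its order in the list it belongs to the marker on the Treatment 1 heading, so its main purpose may be to define Baseline. The flowchart also schedules a photograph after treatment at Visit 3, so not everything is pre-treatment. The match between the VAS and treatment rows points to same-session pain, and the CRF, which may carry the instruction, is not part of the document.

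Much of this stands as evidence of intent, and it limits the severity. It does not remove the conflict. The footnote's wording covers all assessments on treatment days. The Visit 3 photograph row says in its label that it is after treatment, and the VAS row does not. An inferred intention also gives sites no common time for asking.

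A reader might go further and infer that clinician-assessed erythema and adverse events also miss the treatment. The document does not support that. Section 2.2 says: "Physical and dermatological examinations, erythema, and adverse events (such as PIH, burns, etc.) monitoring will be performed and assessed at every visit", follow-up visits included, and the flowchart marks the facial skin examination and adverse events at Visits 1 to 8. Every session, including the last, is therefore followed by a clinician check, and the subject questionnaire covers every session as well. Only a scheduled same-day clinician observation after treatment is absent, and adding one is a preference.

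Nor does it help to set the earliest next treatment visit, 28 − 5 = 23 days after a session, against the 15 days in section 13. That section lists long-lasting scabs as a possible side effect and sets no examination deadline. Scabs and time to resolution are asked of the subject, so the comparison shows no lost data.

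**Conclusion.** Wrong as written; severity moderate. Under the footnote, current-pain VAS scores capture treatment pain for none of the 3 to 5 sessions. Under an unstated recall reading they always miss the last session, and the Visit 1 score refers to nothing. The change-from-baseline analysis in section 11.3 cannot be carried out for VAS under any reading.

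The counts assume that sites follow the footnote literally and that no separate VAS instruction exists outside the document. If the CRF already fixes a post-session time, the data may be sound, but the protocol would still contradict it and the analysis would still not fit.

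A reader might infer that the trial will report near-zero pain in both arms. That is only what literal compliance would tend to produce; the schedule lets an experienced site guess the intended timing. The point does not reach the primary endpoint: FWCS is rated from images by blinded assessors, and taking it before treatment is appropriate.

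**What to change.** 1. Limit the footnote to the wrinkle scales (FWCS, WAS), GAIS, pre-treatment photographs and the baseline or eligibility items.
2. State that VAS pain is recorded after each session, at one fixed time common to both sites and both arms, and refers to that session. State that the Visit 1 value is session-1 pain and not a baseline.
3. Exempt VAS from the change-from-baseline test in section 11.3 and from the comparison of changes in section 11.3.1.9. Compare the session scores themselves between devices, and say which sessions enter: sessions 1 to 3 are scheduled for everyone, while 4 and 5 are optional and depend on response.

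The cost is one footnote, one analysis sentence and some CRF labels. No visits or staff are added. The change has to be in place before subjects are treated, because session pain cannot be collected afterwards.

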10. SAMPLE SIZE CONSIDERATIONS

The rationale for sample size calculation was based on difference between treatments arms in the improvement post treatment in FWCS scores.

$$\text{Improvement} = FWCS_{6 \text{ months}} - FWCS_{Baseline}$$

$$\text{NIM} = Improvement_{Tixel} - Improvement_{Laser} \geq -0.5$$

The assumption that Tixel is non inferior as compared to Laser in the effectiveness as evaluated by FWCS 6 months after first treatment.

FWCS ranges from fine to deep wrinkles in a 1 to 9 scale.

Previous studies demonstrated that the standard deviation of the change in FWCS post 6 months is 0.75.

Assuming that the non-inferiority margin is $\text{NIM} \geq -0.5$, and the $SD = 0.8$ a sample size of 32 completers per group will enable to conclude that Tixel is non inferior to ResuFx with 95% confidence and with 80% power.

Taking into account a dropout rate of 20% a total of 40 cases per group should be recruited. To allow for the possibility of a higher dropout rate a total of 41 cases per group will be recruited.

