11. STATISTICAL METHODS

11.1 General

All measured variables and derived parameters will be listed individually and, if appropriate, tabulated by descriptive statistics.

For categorical variables summary tables will be provided giving counts and percentages.

For continuous variables summary tables will be provided giving count, arithmetic mean, standard deviation, median, 25th and 75th percentile, minimum and maximum of variables by device.

All tests will be two-tailed, and a p-value of 5% or less will be considered statistically significant.

The data will be analyzed using the SPSS version 925.0.

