11.2 Primary Performance Endpoint

FWCS scores will be summarized per subject and time point. Changes from baseline to the last follow-up visit will be summarized as well. For analyzing the changes over time within each arm, the Repeated

measures or Friedman paired test followed by Dunn's post hoc test (as appropriate based on Shapiro and Wilk test for normality) will be applied. For comparison between devices two-sample T-test or Non-parametric, Mann-Whitney Rank sum test (as is appropriate) will be applied.

In addition, in order to keep the study's power, data of the two sites will be pooled together and an Analysis of Covariance (ANCOVA) model will be applied for analyzing the primary endpoint, with adjustment to suspected confounders (baseline measure and site).

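### The only written non-inferiority criterion has an inconsistent sign: read literally, it sets no limit on how much worse Tixel may be

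*Combined protocol and SAP*

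**What the plan says.** Section 10 (Sample Size Considerations) contains everything the plan says about the non-inferiority criterion:

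- Improvement is "FWCS_{6 \text{ months}} - FWCS_{Baseline", that is, follow-up minus baseline.
- The direction of the scale is given by "FWCS ranges from fine to deep wrinkles in a 1 to 9 scale", so a lower score is better.
- The criterion is that "Improvement_{Tixel} - Improvement_{Laser" be at least -0.5. The same bound, with the same sign, is repeated where the sample size is justified.
- The stated purpose is that 32 completers per group "will enable to conclude that Tixel is non inferior to ResuFx with 95% confidence and with 80% power".

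The statistical methods give no second version of the criterion. Section 11.1 says "All tests will be two-tailed, and a p-value of 5% or less will be considered statistically significant". Section 11.2, on the primary endpoint, says "Changes from baseline to the last follow-up visit will be summarized as well" and "For comparison between devices two-sample T-test or Non-parametric, Mann-Whitney Rank sum test (as is appropriate) will be applied", and adds an ANCOVA adjusted for baseline and site. It gives no margin, no direction and no confidence-limit rule.

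**The concern.** The definition of improvement, the direction of the scale and the sign of the bound cannot all stand alongside a non-inferiority aim. With follow-up minus baseline on a scale where higher is worse, a positive Tixel-minus-laser difference means that Tixel did worse. A lower bound of -0.5 on that difference restricts only a superior Tixel.

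In a plan whose analysis section held a complete non-inferiority rule, a sign slip in the sample-size section would be cosmetic. Here section 10 is the only source, so whoever declares non-inferiority must take the criterion from it. Section 11.2 works with changes from baseline, which are naturally computed in the same direction as the printed formula. An analyst who computes the change that way and applies the printed bound runs the wrong test. The planned two-tailed p-values would not reveal this, because reversing the sign of every change leaves them the same. If the analyst instead corrects the sign silently, the direction of the primary criterion is settled outside the written plan, possibly after the results are known.

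**Working it through.** **1. Reproduce the stated sample size.** Inputs from section 10: margin 0.5, SD 0.8, power 80%. A true difference of zero is assumed. The formula is n per arm = 2 × [(z_α + z_0.80) × SD / margin]².

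- One-sided 5%: 2 × [(1.645 + 0.842) × 0.8/0.5]² = 31.65, so 32. This is the plan's figure, and 32/0.8 = 40 matches its dropout allowance.
- One-sided 2.5%: 2 × [(1.960 + 0.842) × 0.8/0.5]² = 40.19, so 41.

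Only the size of the margin enters the formula, so n is the same for either sign.

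**2. Apply the criterion literally to two illustrative cases.**

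| Laser | Tixel | Laser change | Tixel change | Tixel - laser | At least -0.5? |
|---|---|---|---|---|---|
| 5 to 3 | 5 to 5 | -2 | 0 | +2 | Yes: passes, though Tixel did nothing |
| 5 to 4 | 5 to 3 | -1 | -2 | -1 | No: fails, though Tixel is better |

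**3. Size of the effect.** Let D be the true Tixel-minus-laser difference in (6 months - baseline) FWCS, so D > 0 means Tixel is worse. Section 10 does not say which confidence limit is compared with the bound, or whether its 95% is one-sided or two-sided, so both one-sided levels are shown. Assumptions: 32 per arm, SD 0.8, SE = 0.8 × √(2/32) = 0.20, df = 62, non-central t.

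- Written rule: the lower limit of D exceeds -0.5, with non-centrality (D + 0.5)/0.20.
- Direction-consistent rule: the upper limit of D is below +0.5, with non-centrality (0.5 - D)/0.20.

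At D = +0.5 these non-centralities are 1.0/0.20 = 5 and 0/0.20 = 0.

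| True state | Written, 2.5% | Consistent, 2.5% | Written, 5% | Consistent, 5% |
|---|---|---|---|---|
| Tixel 0.5 worse | 99.85% | 2.5% | 99.95% | 5.0% |
| Tixel 0.25 worse | 95.8% | 23.3% | 98.0% | 34.1% |
| No difference | 69.2% | 69.2% | 79.6% | 79.6% |
| Tixel 0.5 better | 2.5% | 99.85% | 5.0% | 99.95% |

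With no true difference the two rules pass equally often, but not in the same trials. In 2,000,000 simulated trials they gave opposite verdicts in 61.5% (one-sided 2.5%) and 40.7% (one-sided 5%).

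**4. Sensitivity.** At 0.5 worse, the written rule still passes with probability 99.95% or more if the SD is 0.75 (the value section 10 cites from previous studies) or if there are 41 per arm. If the bound is applied to the point estimate alone, the figures at 0.5 worse are over 99.99% (written) and 50% (consistent). A normal approximation at one-sided 5% gives 99.96% against 5.0%.

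**The case against.** The best counter-argument is that this is a recoverable slip of notation. The word improvement, the negative margin and the stated aim agree once positive means better, and section 10 says in words that the conclusion sought is non-inferiority. A competent analyst would probably apply the intended direction. The sample size, randomisation and data collection are untouched. This stands, but it describes what a reader would infer, not what the plan says.

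It can also be said that the rest of the plan gives some protection. Sections 11.1 and 11.2 call for summaries by device, which would show the device with the larger reduction. The two-tailed comparison would find a Tixel truly 0.5 worse to be significantly worse in about 69% of trials, and one 0.25 worse in about 23% (same SE and df). That is correct. The statement that there is no limit on inferiority therefore applies to the criterion itself, not to everything the trial would report. A difference test is still no substitute for a margin: at 0.25 worse it would usually be silent.

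Third, the pass probabilities depend on a confidence-limit rule that the plan does not state. This is also correct. They are conditional on literal application and are not a forecast of the trial's error rate. The two worked cases prove the contradiction without them.

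Finally, the missing decision rule in section 11.2 is a separate omission, and correcting the sign would not cure it. That is so, but the omission is why the sign matters here: no other statement exists to override section 10.

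**Conclusion.** The point holds. This is an inconsistency of direction and not an error in the sample-size calculation, since the stated 32 per group reproduces at one-sided 5%. As printed, the trial's only non-inferiority threshold fails a Tixel that is better by more than 0.5 and accepts one that is worse by any amount. Applied literally through a one-sided confidence limit with 32 per arm and SD 0.8, it passes a Tixel that is 0.5 worse with probability 99.85% to 99.95%, where 2.5% to 5.0% is intended.

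That the error is a transposed subtraction is an inference, though a strong one. The contradiction itself follows from section 10 alone, and nothing in section 11 resolves it. It must be corrected before the primary analysis, because it concerns the study's central claim.

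**What to change.** In section 10, do one of the following:

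- define improvement as baseline FWCS minus 6-month FWCS and keep the bound of -0.5; or
- keep the change as written and require the upper confidence limit of Tixel change minus laser change to be below +0.5.

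Then add an explicit primary decision rule to section 11.2. It should give the signed difference, the 0.5 margin, the confidence limit compared with it, the one-sided level of that limit, and the model that supplies the estimate, for example the planned ANCOVA adjusted for baseline and site.

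The cost is one line in section 10 and one or two sentences in section 11.2. Conduct is unaffected, and the sign correction does not change the sample size. The one-sided level does bear on it: 32 completers per group corresponds to one-sided 5%, whereas one-sided 2.5% would need 41. The level written into section 11.2 should therefore be chosen with that in view.
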